13.4 Procedures for reporting deviation(s) from the original SAP

These will be submitted as substantial amendments where applicable and recorded in subsequent versions of the protocol and SAP.

14 Analysis

14.1 Main analysis

A detailed statistical analysis plan will be written prior to analysis. The reporting of findings will be in accordance with the CONSORT guidelines for cluster RCTs (29) and SPIRIT recommendations for reporting trials of interventions.(32) Statistical analysis will be performed in R or Stata (version 13 or higher).

All analyses will be intention to treat (i.e. students will be analyzed in the groups to which they were randomised, regardless of adherence to the intervention) and missing outcome data will not be replaced. Statistical tests and confidence intervals (CI) will be two-sided. Between-group comparisons will be presented with 95% confidence intervals wherever possible. As the trial includes a reasonable number of clusters, the analysis will be based on the individual student, allowing for clustering between students within school using robust standard errors. All analyses will control for baseline outcomes (if applicable), school level stratification variables (proportion of children eligible for FSM: country-specific median, geographical area) and student characteristics (age, gender, parental employment status).

Primary outcome: Multilevel logistic regression models will be used to compare the lifetime use of illicit drugs at 24 months by arm, and results presented as odds ratios and 95% CIs. Intra-cluster correlations (ICCs) alongside 95% CIs will also be reported.

Secondary outcomes: Multilevel linear (continuous outcomes) and logistic (binary outcomes) regression models will be used to compare secondary outcomes.

Sub-group analyses: Primary sub-group analyses will investigate the effect of the intervention on the frequency of any and specific drug use in a sub-group who report ever having used drugs at baseline. To examine the effect of the intervention on inequalities intervention effects in the following sub-groups: 1) school-level FSM entitlement above versus below country level median), 2) student-level FSM eligible versus not eligible, 3) parental employment status, and 4) gender. We will also estimate intervention effects in the following sub-groups to examine the impact of context and the hypothesized mechanisms of action: 5) geographical area, 6) peer supporter status, and 7) having had an opportunity to use drugs. Interactions between the trial arm and these variables will be modelled. We will also estimate the proportion of drug use which is recanted (where baseline lifetime drug users respond they have never used at follow-up) as a measure of reliability. The results of these exploratory analyses will be presented using confidence intervals.

Missing data: Baseline characteristics of students who have complete primary outcome data and those who do not will be compared. Multiple imputation will be performed to assess the impact of missing outcome data using MICE (Multivariate Imputation by Chained Equations) implemented using the ICE routine in Stata. Imputation models will include outcomes, intervention arm, stratifying variables and a main school effect to allow for clustering, as well as any appropriate baseline covariates. The main analyses will be repeated on the imputed datasets. Another sensitivity analysis will be conducted assuming all those lost to follow-up have used drugs.

Process outcomes: Multilevel linear and logistic regression models will be used to compare the hypothesised mediators of change outlined in our logic model (see appendix 1) at the 24-month follow-up. For the primary outcome, an interaction term will be fitted between allocation and ever having visited www.talktofrank.com, the perceived prevalence of drug use in the year group (anyone has used vs. no-one), having a conversation with school friends about drugs (ever vs. never), and ever receiving a drug offer.

15 **Process evaluation**

Informed by the Medical Research Council's guidance(33), an embedded process evaluation will be conducted. The process evaluation will explore the following issues:

- Fidelity during the training and intervention delivery. Drawing on Caroll et al's multicomponent model for measuring fidelity, (34) and tools developed in the pilot, ³³ adherence to the intervention manual will be examined, as well as the extent to which training is standardised, and variations in quality of delivery across different schools and geographical areas.
- Intervention reach and reception. The proportion of students who report a conversation about drug related harms or harm minimisation in each arm will be compared. The receipt of the intervention and extent to which key intervention messages are evident with students who are and are not peer supporters will be examined.
- Contamination. Schools' activities related to drug use will be audited and interviews conducted with school staff to examine any changes to usual practice that might result due to participation in the trial.
- Acceptability of the intervention: to students who are and are not peer supporters, staff
 within schools including members of the senior management team, and public health
 practitioners who have delivered the intervention.

• Mechanisms of action, specifically whether the intervention worked as hypothesised in the logic model (see appendix 1) and whether this varied across trial centres and schools.

Table 2 summarises the data to be collected and issues addressed. In-depth qualitative data will be collected from four 'case study schools' which receive the intervention where more extensive evaluation will be undertaken at each centre (West of England and South Wales) using structured observations of training, interviews with trainees', and interviews with teachers on the senior management team.

Table 2. Summary of the process evaluation

Data source, method, sampling and timescale	Key areas covered	Issues
		addressed
Structured observation of training of trainers and	Trainees' responses,	Intervention
peer supporters training (2 observations of	adherence to manual.	fidelity,
training of trainers, 6 observations of peer		acceptability
supporter training (mix of the full 2 days and 4		
follow-ups)).		
10 interviews with peer supporters (or pairs of	Trainees' experience of the	Acceptability,
peer supporters) and 6 interviews with trainers in	training, contextual barriers	mechanisms of
each case study school, ~ 1 month of being	and facilitators, impact on	change, reach,
trained with 5 occurring ~ 1 month of end of 10-	them and others.	fidelity,
week intervention delivery. ^a		sustainability
6 focus groups, with a random sample of nonpeer	Awareness of and exposure	Reach,
supporter students in each case study	to the intervention,	acceptability,
school ~1 month after 10-week intervention	perception of intervention,	fidelity,
period.	impact on them and wider	mechanisms of
	school life.	change.
Intervention delivery staff (trainers) and peer	Trainees' response,	Intervention
supporter training evaluation forms. Attendance	adherence to intervention,	fidelity,
registers of training and follow-up sessions to	receipt of training.	acceptability
examine proportion of peer supporters who attend		
all sessions. All intervention schools.		
Questionnaire at 24-month follow-up to students	Exposure to the	Intervention
in all schools.	intervention, whether	reach,
	students report a	acceptability,

	conversation about harms\	mechanisms of
	harm minimisation.	change,
		contamination.
Audit of school policies and procedures at	Relevant drug prevention	Contamination,
baseline and the 24-month follow-up.	policies or practices for	mechanisms of
Questionnaires with school PSHE leads. All	dealing with drug use.	change,
schools.		sustainability.
Interviews with member of senior management	Awareness of and	Intervention
team (SMT) in all four case study schools ~6	experience to the	sustainability,
months of end of 10-week intervention period. ^a	intervention, perception of	acceptability,
	intervention.	mechanism of
		change.
School records of student attendance in all	Whether any students	Contamination.
schools at 24-month follow-up.	moved from intervention to	
	control schools.	

^a Or until data saturation is reached.

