6.1 Risk assessment

A Trial Risk Assessment has been completed to identify the potential hazards associated with the trial and to assess the likelihood of those hazards occurring and resulting in harm. A copy of the trial risk assessment may be requested from the CTR, Cardiff Trial Manager. The trial is low risk.

Participant risks: Potential risks of the intervention to participants are minimal. Some individuals might find aspects of intervention content or research upsetting if they, or a significant other, have experienced a problem in relation to drug use. Trial managers will work with schools to ensure a system is in place to enable appropriate support to be provided in such circumstances. Any potential for harmful effects due to the intervention itself will be explored via the collection and analysis of qualitative data to explore unintended consequences.

Societal risks: As with any health intervention, there is a risk of widening health inequalities if the students that are exposed to the intervention are at a lower risk of drug use. We propose to examine the effect of FRANK friends on socioeconomic inequalities in illicit drug use operating at the parental and school-level.

7 School and Participant selection

School and participants are eligible for the trial if they meet all of the following inclusion criteria and none of the exclusion criteria apply. All queries about school and participant eligibility should be directed to the Trial Manager(s) before the sign a memorandum of understanding.

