8.1 School identification

The trial will be conducted in two geographical areas (South Wales and the West of England), which will enable exploration of the generalisability of the findings. All state secondary schools within a one and half hours travel time from the recruiting centres based in CTR Cardiff and the University of Bristol will be eligible for inclusion in the sampling frame. 48 schools will be included (24 from each geographical area).

A list of eligible secondary schools will be obtained (one for Wales and one for England). These will be anonymised and an ID, area, and the proportion of students with the school that are entitled to receive free school meals (FSM) (based on the latest available figures) retained and passed to the trial statistician (TS) who will be blinded to any identifiable information. All schools will be organised into the two geographical areas and stratified according to the median FSM entitlement for that country. Within each strata the order of schools will be randomly shuffled. IDs will be passed on to TMs so schools can be identified. Initially the first listed schools within each stratum will be selected. If schools decline or do not respond, TMs will select the next school(s) listed within each stratum until all are recruited.

Eligible schools will be approached via a relevant senior manager (deputy head, head of pastoral care), identified with the help of the Schools Health Research Network in Wales and Public Health leads for schools in local authorities in England, and invited to participate in the FRANK friends study. Schools will be emailed or posted a project information sheet, reply envelope and form indicating if they wish to participate. If necessary, non-responders will be followed up with a reminder and then by a phone call by the Trial Manager(s). All interested schools will be visited by the Trial Manager for that geographical area and a contact from the intervention delivery team to discuss the trial in more detail and agree a research contract including signing a memorandum of understanding (MoU) describing the roles, responsibilities, timeline of intervention delivery, and assessments before taking part in

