8.3 Randomisation

Randomisation will be completed at school-level. Randomisation will be coordinated centrally by the CTR. The randomisation schedule will be stratified and will be prepared and held by an independent statistician within the CTR. Within each of the two countries, schools will be organised into the two FSM strata. Each school will be assigned an ID number, after which an independent statistician will randomly allocate schools within each stratum to one of two arms using random block allocations. Block sizes of 2, 4 and 6 will be used. Further detail on this will be included in the unblinded randomisation protocol.

9 Withdrawal & losses to follow-up

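### School-level inequality is tested with free-school-meal entitlement cut at the country median, which loses some power if the effect follows a gradient (minor)

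*Protocol*

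**What the plan says.** Section 6.1 of the protocol treats widening health inequality as the societal risk and gives this undertaking: "We propose to examine the effect of FRANK friends on socioeconomic inequalities in illicit drug use operating at the parental and school-level". Section 14.1 carries it out through sub-group analyses. Item 1, the only listed sub-group that measures school-level deprivation, is "school-level FSM entitlement above versus below country level median". On method, the section says "Interactions between the trial arm and these variables will be modelled". On status it says "The results of these exploratory analyses will be presented using confidence intervals".

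The same median is used elsewhere:
- Sampling: schools are "stratified according to the median FSM entitlement for that country" (section 8.1).
- Randomisation: "Within each of the two countries, schools will be organised into the two FSM strata" (section 8.3).
- Adjustment: the models include "proportion of children eligible for FSM: country-specific median, geographical area" (section 14.1).

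Section 8.1 also has each eligible school's FSM proportion kept and passed to the trial statistician, so the uncut value is available. No power, gradient or FSM distribution is given for this interaction.

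**The concern.** The question is whether the intervention effect changes with school deprivation. A median split treats a school just above the cut like the most deprived school, and a school just below it like the least deprived. The median's roles in sampling, randomisation and adjustment justify it as a design covariate. They give no reason to expect the effect to change at that point.

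The modifier varies only between 48 schools, so information on it is scarce already. If benefit fades gradually as deprivation rises, the cut makes the interval for the interaction wider relative to the signal. A wide interval that includes no difference could then be taken as reassurance on the risk that section 6.1 names.

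**Working it through.** **Inputs from the protocol (sections 13.1, 13.3 and 14.1).** 48 schools, 1:1 allocation, 122 students per school, ICC 0.01, coefficient of variation 0.28, 13.7% attrition, 24.0% vs 18.1% (OR about 0.70), two-sided 5%.

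**Assumed, because the protocol is silent.** The shape of the FSM distribution, a linear gradient in the log OR, its size per SD of FSM, and 12 schools in each area-by-FSM stratum.

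**1. The protocol's own figure.** Two proportions at 90% power with continuity correction need 1035 per arm. The design effect is 1 + ((1 + 0.28²) × 122 − 1) × 0.01 = 2.306. Then 2 × 1035 × 2.306 / 0.863 + 122 (one extra school) ≈ 5652, against 5655 stated. The inputs are read correctly.

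**2. Precision of the interaction.**
- Analysed students per school: 122 × 0.863 = 105.3, or 24 × 105.3 ≈ 2527 per arm.
- Design effect at that size: 1 + (1.0784 × 105.3 − 1) × 0.01 = 2.125.
- Variance of the log OR: [1/(2527 × 0.24 × 0.76) + 1/(2527 × 0.181 × 0.819)] × 2.125 ≈ 0.0103, so SE ≈ 0.101.
- With balanced arms, this is also approximately the SE of the interaction per SD of a continuous modifier.

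**3. Effect of the cut.** For gradient g per SD, power with continuous FSM is Φ(g/0.101 − 1.96). With the split it is Φ(√r² × g/0.101 − 1.96), where r² is the squared correlation between FSM and its median indicator. It is 0.75 for uniform FSM, 0.637 for normal and 0.624 for beta(2,8).

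| g per SD | continuous | split, uniform | split, normal | split, beta(2,8) |
|---|---|---|---|---|
| 0.15 | 32% | 25% | 22% | 22% |
| 0.20 | 51% | 40% | 35% | 35% |
| 0.25 | 70% | 57% | 51% | 50% |
| 0.30 | 84% | 73% | 66% | 65% |

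The loss is about 7 to 10 points at 0.15 and about 11 to 20 points at 0.25 to 0.30. As a guide to scale, 0.25 per SD around OR 0.70 means 0.70 × e^−0.25 = 0.55 at one SD below the mean and 0.70 × e^0.25 = 0.90 at one SD above.

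Independently of g, the split keeps 75% (uniform) or 64% (normal) of the information. That is like dropping 48 × 0.25 = 12 or 48 × 0.363 ≈ 17 schools for this question. The SE relative to the signal grows by 1/√0.75 = 1.15 or 1/√0.637 = 1.25.

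**4. Simulation of 48 schools at g = 0.25, continuous vs split.** Absolute power depends on how the ICC is translated to the log-odds scale. The loss depends on it much less.
- ICC on the proportion scale: uniform 65% vs 54%, normal 65% vs 46%, beta(2,10) 63% vs 44%.
- Smaller between-school variance (ICC on the log-odds scale): uniform 75% vs 61%, normal 74% vs 55%, beta(2,10) 71% vs 50%.

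These losses are 11 to 21 points. Over gradients from 0.20 to 0.357 the simulated loss was 10 to 14 points for uniform FSM, 13 to 20 for normal and 14 to 23 for beta(2,10). Simulation error is about one point on each power figure.

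**5. If FSM also predicts drug use.** FSM variation within each half then becomes noise under the split. With an assumed slope of 0.2 log-odds per SD and g = 0.25, power was 72% vs 51% (uniform), 72% vs 40% (normal) and 71% vs 41% (beta(2,10)), a loss of 21 to 32 points. Over gradients of 0.25 to 0.36 the range is about 17 to 33.

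**6. If the effect steps at the median.** With normal FSM and the same size of effect, the split has 76% power and continuous FSM 54%.

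**The case against.** The median is not arbitrary. It is the sampling stratum, the randomisation stratum and an adjustment term, so the arms are balanced within each half. Sub-grouping on a stratification factor is conventional and needs no linearity assumption. The analysis is labelled exploratory, reported by confidence interval, claims no power, and is one of seven listed effect modifiers. Section 14.1 also examines student-level FSM and parental employment, so the inequality question does not rest on item 1 alone. For a weak gradient the analysis would usually miss the effect either way: even continuous FSM has only about 32% power at 0.15 per SD. The planned adjustment for baseline outcomes and parental employment may also absorb part of any FSM main effect, which would soften step 5.

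All of this stands and lowers the severity. It does not remove the loss under a gradient, since precision is what a confidence interval reports.

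A reader might infer that the cut costs a fixed 15 to 35 points of power. The documents do not support that, because they give neither the FSM shape nor the gradient. Without an FSM main effect, a 35-point loss needs r² of about 0.43 or less, which means strongly right-skewed FSM. A reader might also infer that the plan breaks its section 6.1 undertaking or contradicts itself. It does neither: item 1 does examine school-level inequality, only less efficiently than the data allow.

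**Conclusion.** Holds as a minor, conditional efficiency weakness. With a roughly linear gradient on the log-odds scale and uniform, normal or mildly skewed FSM, the median split loses about 6 to 10 power points at 0.15 per SD and about 10 to 21 points at 0.25 to 0.36 per SD. The loss rises to about 17 to 33 points at those stronger gradients if FSM predicts drug use at 0.2 log-odds per SD. The gradients, the FSM shapes and that slope are all assumptions. If the effect steps at the median, the planned split is better. Nothing in the protocol is misstated, and the primary analysis is untouched.

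**What to change.** For item 1 of the sub-group analyses in section 14.1, or in the statistical analysis plan before outcome data are analysed:
- Make the interaction between arm and the school's FSM percentage (continuous, centred within country, with FSM percentage also as a main effect) the school-level inequality test.
- Report the interaction OR with its 95% CI, and the intervention OR at a prespecified low and high FSM value.
- Keep the above/below-median ORs as a prespecified display and a rough check on linearity.
- Keep the median stratum and area as adjustment terms.

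The cost is a short change of text and no new data. The downside is the linearity assumption, and some loss of power if the effect really does step at the median. Fixing the modifier in advance matters, because a later change would look data-driven.

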4.1 Existing research

A number of school-based interventions have focused on preventing student drug use. Three systematic reviews have found these interventions are associated with modest improvements in knowledge about drugs, but few had an impact on drug use after 12 months.(17)(18)(19) The latest Cochrane systematic review of universal school-based interventions to prevent illicit drug use (comprising 51 randomised control trials (RCTs), 2 in the UK) found those that attempted to increase social competences (i.e. teaching selfmanagement, social skills, problem-solving) and those based on social influence theories (i.e. correcting overestimates of drug prevalence) had the largest effects on drug use.(17) One NIHR funded systematic review found Positive Youth Development interventions had little effect on illicit drug use.(20) Another review of school-based peer-led interventions found a small protective effect on cannabis use (3 RCTs) at ≥12 months, suggesting peerled approaches may be promising.(19) In the RCTs evaluating school-based peer-led drug prevention interventions, the Towards No Drug Abuse Network RCT found iatrogenic effects in a sub-group of students whose friends already used alcohol, tobacco and drugs.(21) In the peer-led arm of the EU-Dap trial, there were very low levels of implementation, with only 8% of centres implementing all seven sessions, and 71% not conducting any meetings at all.(22) This suggests that while peer-led approaches are promising, modifications are needed to avoid iatrogenic effects and improve implementation.

These systematic reviews highlight methodological weaknesses in the existing evidence base. These include: small sample sizes, potential contamination,(21) inadequate reporting of randomisation,(17) a failure to account for clustering,(17) (19) a lack of registered protocols and independent evaluation.(23) The lack of registered protocols is a particular problem with substance misuse prevention interventions, as it is often unclear which outcome measure and what time point forms the basis of the primary effectiveness analysis, leading to concerns of outcome switching.

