10.1 The FRANK friends intervention

FRANK friends is a peer-led drug prevention intervention to prevent drug use in UK year 9 secondary school children. FRANK friends has been developed over a 31-month NIHR PHR funded study (PHR - 12/3060/03) comprising intervention development, prototyping and a pilot cRCT.

Based on diffusion of innovations theory,(30) FRANK friends aims to diffuse information from www.talktofrank.com via secondary school students' social networks in UK Year 9 (aged 13-14). Following methods developed in the ASSIST intervention and found to be acceptable in the pilot study, FRANK friends has five stages:

- Nomination of peer supporters: Students in UK year 9 are asked to identify influential peers using three questions, "Who do you respect in year 9 at your school?", "Who are good leaders in sports or other groups activities in year 9 at your school?", and "Who do you look up to in year 9 at your school?" The 17.5% of Year 9 students receiving the most peer nominations are invited to a recruitment meeting;
- Recruitment of peer supporters: A meeting is held with nominees to explain the role of a peer supporter and answer questions. Parental consent is sought for participation in a training course;
- 3. Training of peer supporters: A 2-day training course is held out of school, facilitated by an intervention delivery team. Trainers are typically experienced in youth work and/ or health-promotion and employed by the NHS, third-sector charities, or local government. Trainers provide information on the effects and risks associated with specific drugs, minimising potential harms, and the law from Talk to FRANK. Peer supporters practise communication skills including, listening, negotiation, how to talk with their peer group about drugs, and how to access www.talktofrank.com by computer or smartphone. Methods used to achieve these aims include participatory learning activities such as role plays, student-led research, small group work and discussion, and games;
- 4. Intervention period: Peer supporters are asked to have informal conversations with their peers on drugs, when travelling to and from school, in breaks, at lunchtime, and after school in their free time, and log a record of these conversations in a pro-forma diary. Over the 10-week period four follow-up school visits are made by intervention

delivery staff to meet with peer supporters to provide support, trouble shooting, and monitor peer supporters' diaries;

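### The mechanism analysis fits arm interactions with variables apparently measured after randomisation, so its within-level arm effects, and in some circumstances the interactions, can be spurious

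*Protocol*

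**What the plan says.** The Process outcomes paragraph of Protocol section 14.1 has two parts. First, multilevel models compare by arm the "hypothesised mediators of change outlined in our logic model (see appendix 1) at the 24-month follow-up". Second, for the primary outcome, "an interaction term will be fitted between allocation and ever having visited" the website, and also between allocation and perceived use in the year group, "having a conversation with school friends about drugs (ever vs. never), and ever receiving a drug offer".

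Other sections bear on the status and timing of these variables:

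- Section 10.1: "FRANK friends aims to diffuse information from" the website through students' social networks, and "Peer supporters are asked to have informal conversations with their peers on drugs".
- Section 15, Table 2: exposure to the intervention and reports of conversations about harms come from the "Questionnaire at 24-month follow-up to students" in all schools, with mechanisms of change among the issues addressed.
- Section 14.1, opening paragraphs: all models adjust for the baseline outcome where there is one, the stratification variables, age, gender and parental employment. No other confounder is named.

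The sentence that labels results as exploratory closes the Sub-group paragraph, not the Process outcomes paragraph.

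**The concern.** Randomising schools makes the arms comparable as a whole. It does not make them comparable within groups that form after allocation. If the intervention sends new students to the website or into conversations, visitors in intervention schools and visitors in control schools can be different kinds of student. An arm contrast among visitors then mixes any effect of the intervention with that difference in make-up.

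At stake is how the trial explains its result. A favourable odds ratio among students who visited or talked would invite the conclusion that the intervention works in those it reaches, even after a null primary result. The protocol already fixes the outcome, the four variables and the form of the model, and cut-points for most of them, so this is a stated choice and not a detail left open for the SAP.

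**Working it through.** **Size of the trial.** The protocol gives no figure for this analysis, so its sample size is reproduced first to set the scale. Inputs from section 13.3: 24.0% vs 18.1%, 90% power, two-sided 5%, 122 students per school, ICC 0.01, coefficient of variation 0.28, attrition 13.7%.

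- Per arm without clustering (unpooled variance): 998.
- Design effect: 1 + ((1 + 0.28²) × 122 − 1) × 0.01 = 2.306.
- Schools per arm: 998 × 2.306 / 122 = 18.86, rounded up to 19, plus 1 = 20.
- Students: 2 × 20 × 122 / 0.863 = 5655, as stated. Schools: 20 / 0.863 = 23.2, rounded up to 24 per arm, so 48, as stated.
- Expected with follow-up: 5655 × 0.863 = about 4,880.
- Planned odds ratio: (0.181/0.819) / (0.240/0.760) = 0.70.

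**Set-up of the examples.** Half the students are high risk and half low risk. Risk is unmeasured, and arm has no effect on drug use in anyone, so every true odds ratio is 1.00. Overall use is 24% in both arms. The risk split, the use rates by risk, and all visit and conversation rates are assumptions, not protocol figures.

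Within a level of the variable, P(use) = Σ P(risk group | level, arm) × P(use | risk group). The odds ratio compares intervention with control.

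**Example 1: conversations.** Use is 34% (high risk) and 14% (low risk). Conversations are 50%/10% (high/low) in control and 80%/40% in intervention.

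- Had a conversation: share at high risk 0.5/0.6 = 0.833 in control and 0.8/1.2 = 0.667 in intervention. Use 30.7% vs 27.3%. OR = 0.376/0.442 = 0.85.
- No conversation: share at high risk 0.5/1.4 = 0.357 and 0.2/0.8 = 0.25. Use 21.1% vs 19.0%. OR = 0.235/0.268 = 0.87 (0.875 to three places).
- Ratio of odds ratios: 0.850/0.875 = 0.97.

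Both stratum effects are wrong, but the interaction barely moves. With about 4,880 students the standard error of the log ratio is about 0.14 before clustering, so z is about 0.03/0.14 = 0.2.

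**Example 2: website visits, with a change in who visits.** Use is 40% (high risk) and 8% (low risk). Visits are 30%/10% in control and 50%/50% in intervention.

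- Visitors: control (0.3 × 0.40 + 0.1 × 0.08)/0.4 = 32%; intervention 24%. OR = 0.316/0.471 = 0.67.
- Non-visitors: control (0.7 × 0.40 + 0.9 × 0.08)/1.6 = 22%; intervention 24%. OR = 0.316/0.282 = 1.12.
- Ratio: 0.67/1.12 = 0.60.

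The odds ratio among visitors is about the planned 0.70, with no effect present.

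**Simulation.** 1,000 trials per case; 48 schools of 102 students (4,896); ICC 0.01; logistic model with school-clustered standard errors; no baseline covariates; no arm effect on use; use rates as in Example 2.

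| Visits in intervention (high/low risk; control 30%/10%) | OR visitors | OR non-visitors | Ratio | Interaction p<0.05 | Visitor effect p<0.05 |
|---|---|---|---|---|---|
| 50%/50% | 0.67 | 1.12 | 0.60 | 92% | 86% |
| 40%/30% | 0.76 | 1.05 | 0.72 | 58% | 55% |
| 30%/10% (not affected by arm, as at baseline) | 1.00 | 1.00 | 1.00 | 7% | 7% |

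The overall arm test rejects in 6% in all three rows, so the excess in the first two comes from conditioning on a variable that the arm has changed.

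**Uniform shift.** In further simulations the intervention raised visits by 10 to 30 points and left their dependence on risk unchanged on the logit scale. The interaction test stayed near nominal (5% to 10%). Stratum odds ratios ranged from 0.98 to 0.65, with rejection from 5% to 97%, depending on the size of the shift and the strength of the shared cause.

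**The case against.** The strongest reply has four parts.

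**The timing is inferred.** The interaction sentence gives no measurement time, the logic model is not shown, and Table 2 places only exposure and conversations in the 24-month questionnaire. This stands as a limit. Still, the sentence just before sets the 24-month time point, and section 10.1 makes website content and conversations explicit targets. Intent to change is less explicit for perceived use and drug offers.

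**The protocol plans an interaction term, not stratum effects, and under a uniform shift that term is nearly null.** This also stands: Example 1 harms the stratum effects only. The interaction is distorted when the intervention changes which students visit or talk, and a peer-led programme could plausibly do that. An interaction is also hard to interpret without reading the arm effect at each level.

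**The examples ignore adjustment.** Baseline drug use is an obvious proxy for risk and would remove part of the bias. The sizes above are therefore unadjusted illustrations.

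**The protocol never says that the interaction tests mediation.** That is so, and the point does not depend on it.

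Three stronger readings are tempting. A reader might infer certain bias in every stratum; there is none without a shift, or without a shared cause left after adjustment. A reader might fault sub-group 7 (opportunity to use drugs) in the same way; its time point is simply unstated, which is a minor clarification. A reader might argue that baseline versions of these items would address the harm reported in section 4.1 among students whose friends already used. The four items do not measure friends' use, and section 14.1 already plans a quantitative sub-group of students who had used drugs at baseline.

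**Conclusion.** The point holds for the Process outcomes analysis. As most naturally read, it conditions on post-randomisation variables, at least two of which the intervention is meant to change. With no true effect, stratum odds ratios can be 0.85 and 0.87, and the interaction can be as far off as 0.67 against 1.12 (ratio 0.60).

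These sizes rest on assumed risk, visit and conversation rates and on no covariate adjustment. Bias needs both a shift caused by the arm and a shared cause that remains after adjustment. A spurious interaction further needs a change in which students visit or talk. The direction and size in this trial cannot be known from the protocol.

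The primary comparison, the sample size and the significance level are untouched. The analysis should be corrected because its results would be used to say how the intervention works.

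**What to change.** In section 14.1, Process outcomes, and in the SAP:

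1. Keep the comparison of these variables by arm at 24 months. It is a randomised comparison.
2. For effect modification, use the baseline values of the same items wherever the baseline questionnaire collects them.
3. If a mechanism is to be claimed from the 24-month values, use a causal mediation model with the confounders stated and a sensitivity analysis for unmeasured confounding.
4. Otherwise report the 24-month interactions only as exploratory, non-causal associations, and say so in that paragraph.
5. State the time point of sub-group 7 as a clarification.

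The cost is wording, plus adding any missing item if the baseline questionnaire is still open. Where an item was not collected at baseline, only options 3 and 4 remain for it. The small downside is that modification by actual exposure is no longer reported as an effect of the intervention. Baseline modifiers answer who benefits and not how, which is why steps 1 and 3 stay alongside step 2.
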